12.3 Multiple Comparisons/Multiplicity

No multiplicity adjustment will be applied.

12.4 Withdrawals, Dropouts, Loss to Follow-up

The Investigator may withdraw any subject from the study at any time for medical reasons or if the subject is unable or unwilling to comply with the protocol. A subject may elect to discontinue his/her participation and withdraw from the study at any time. A subject withdrawing from the study may do so without detriment to access to medical care. See Sections 6.5 - 6.6 of the protocol for more details on withdrawal of subjects.

Any subject discontinuing from the trial at any time other than the screening period will not be replaced. A subject who receives the investigational product but withdraws for any reason will be encouraged to return for the safety assessments according to the Schedule of Procedures (Appendix 1). If the subject does not wish to remain in the study, the subject can choose to withdraw consent and discontinue at any time as outlined in Section 6.5 of the protocol.

12.5 Missing, Unused, and Spurious Data

In general, there will be no substitutions made to accommodate missing data points. All data recorded on the eCRF will be included in data listings that will accompany the CSR.

When tabulating AE, Concomitant Medications and Hospitalizations data, partial dates of event onset will be handled as follows:

• If the day of the month is missing, the onset date will be assumed to be the date of the Day 0 vaccination or first of the month, whichever is later, in order to conservatively report the event as vaccine-emergent.

- If the month or year (or both) of the onset date is missing, impute month or year (or both) which makes the imputed date most adjacent to the first dosing date.
- If the onset day and month are both missing, the event onset will be coded to the date of the Day 0 vaccination or 1st January of the year, whichever is later, in order to conservatively report the event as vaccine-emergent.
- A completely missing onset date will be coded as the date of the Day 0 vaccination, unless the end date suggests it could have started prior to this in which case impute the 1st January of the same year as the end date.
- When imputing a start date ensure that the new imputed date is prior to the end date of the AE or med.

A conservative approach will be taken to assess the relationship of an event to test article: if the relationship of an event is missing, it will be considered treatment-related. Missing severity for an AE will not be imputed.

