6.2 Concomitant Medication

The assessment of concomitant medication use by the subject during the study will coincide with the collection period of adverse events; per the protocol, concomitant medication includes prescription and non-prescription drugs or other treatments, and any vaccine other than study vaccines. Concomitant medications recorded on the Concomitant Medications CRF will be summarized by WHO-DRUG Anatomical Therapeutic Chemical (ATC) Term and standardized (generic) medication name version September 2019. The number (percentage) of subjects who record one or more concomitant medications will be presented by treatment group for all subjects in the Safety Population. Multiple occurrences of medication usage for a subject will be counted only once within an ATC term and standardized medication name. The presentation of concomitant medications will include all medications recorded on the Concomitant

Medications CRF, including medications with a missing or partial start date or a start date prior to Study Day 0 vaccination. A separate listing of treatment-emergent new concomitant medications will be presented.

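### SAP 12.5 gives a Day 0 start to medications already known to have begun before vaccination, and its rules for year-only and wholly missing dates need tightening

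*SAP*

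**What the plan says.** SAP 12.5 sets one list of rules for three kinds of record: "When tabulating AE, Concomitant Medications and Hospitalizations data, partial dates of event onset will be handled as follows". In order, the bullets are:

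1. Day missing: "the onset date will be assumed to be the date of the Day 0 vaccination or first of the month, whichever is later".
2. Month or year (or both) missing: "impute month or year (or both) which makes the imputed date most adjacent to the first dosing date".
3. Day and month missing: "the event onset will be coded to the date of the Day 0 vaccination or 1st January of the year, whichever is later".
4. Onset wholly missing: "A completely missing onset date will be coded as the date of the Day 0 vaccination". An exception applies where the end date points to a possible earlier start, "in which case impute the 1st January of the same year as the end date".
5. A guard: an imputed start has to fall before the end date.

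Bullets 1 and 3 give their reason, which is to err towards counting the event as vaccine-emergent. Bullets 2 and 4 give none.

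Two outputs can depend on these dates. SAP 6.2 plans an overall medication summary, "including medications with a missing or partial start date or a start date prior to Study Day 0 vaccination", and then adds: "A separate listing of treatment-emergent new concomitant medications will be presented". SAP 8.1.2 builds the 21-day unsolicited AE dataset from start dates that run from Day 0 to Day 22 at the latest.

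**The concern.** Dating an event of unknown timing to Day 0 is ordinary caution. Bullets 1 and 3 go further. They apply the same treatment when the recorded month or year already shows that the start came before vaccination, so a known fact is overwritten. For a medication this has no safety benefit. It makes a long-standing drug look newly started after the vaccine, in a listing meant to show exactly which drugs were new.

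Two wording problems sit beside it. A year-only start meets the condition of both bullet 2 and bullet 3, and nothing says which governs. The exception in bullet 4 has no defined trigger, so two programmers could date the same AE differently, and the 21-day AE profile is part of the primary safety endpoint.

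**Working it through.** The plan states no figure on this point, so there is nothing to reproduce. The check applies the rules to example dates.

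**Assumption.** The documents give no calendar date for Day 0. I take 1 September to 30 November 2017, judged from the document dates and the 2017-18 season, with 1 October 2017 as the worked example.

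**Bullets 1 and 3.** Imputed start = max(Day 0, first day of the known month or year).

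| Recorded start | Bullet | Calculation | Result |
|---|---|---|---|
| June 2012 | 1 | max(1 Oct 2017, 1 Jun 2012) | Day 0 |
| May 2017 | 1 | max(1 Oct 2017, 1 May 2017) | Day 0 |
| 2010 | 3 | max(1 Oct 2017, 1 Jan 2010) | Day 0 |
| 2016 | 3 | max(1 Oct 2017, 1 Jan 2016) | Day 0 |

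The result is the same for any Day 0 in the assumed range, because a period that ended before vaccination can never supply the later date. The guard in bullet 5 rules out a Day 0 start only for a medication that stopped on or before Day 0. It does nothing for one that is ongoing or stops after Day 0.

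**Bullet 2 against bullet 3, year only known.**
- 2016: bullet 2 gives the date in 2016 nearest to dosing, which is the end of December 2016. Bullet 3 gives Day 0. They conflict.
- 2017: both give Day 0.
- 2018: both give 1 January 2018.

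The conflict is therefore confined to years before the year of vaccination. There, one bullet keeps the start before vaccination and the other moves it to Day 0.

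**Bullet 4.** Two readings of the exception are possible. The narrow one applies it only when the end date is before Day 0. The broad one applies it to any known end date, since almost any such event could have begun earlier.

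| End date | Narrow reading | Broad reading |
|---|---|---|
| Missing | Day 0 | Day 0 |
| 2017, before Day 0 | 1 Jan 2017 | 1 Jan 2017 |
| 2017, on or after Day 0 | Day 0 | 1 Jan 2017 |
| 2018 | Day 0 | 1 Jan 2018 |

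Over the assumed range, 1 January 2017 is Day -243 to Day -333, and 1 January 2018 is Day 32 to Day 122. With Day 0 on 1 October 2017 they are Day -273 and Day 92. All lie outside Days 0 to 22. Under the narrow reading only events that ended before vaccination leave the window, which is correct. Under the broad reading post-vaccination AEs leave it too. Those dated to 1 January 2017 also cease to be treatment-emergent, while those dated to 1 January 2018 stay within Days 0 to 364.

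**The case against.** The case on the other side is substantial, and most of it stands.

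- **AEs and hospitalizations are hardly touched by bullets 1 and 3.** Protocol 8.1 collects AEs from consent, Protocol 6.3 collects hospitalizations from the day of consent, and Protocol 6.1.1 places consent on the day of planned vaccination. Such a record should rarely carry an earlier month or year. This stands and leaves medications as the real case.
- **Only one supporting listing is exposed.** The overall summary in SAP 6.2 takes every recorded medication whatever its start date. SAP 12.5 also puts all recorded eCRF data in the listings, so the partial date should remain visible. SAP 6.2 does not say that the new-medication listing is selected on imputed dates. This stands, so the consequence is conditional.
- **A reader might infer that every pre-trial medication with a missing start day is misdated.** The guard prevents that for drugs that ended before Day 0. Nor do the documents say how often start dates are partial.
- **A reader might infer that wholly unknown AE onsets are pushed out of the 21-day window, against a stated conservative aim.** The documents do not support this. The default is Day 0, inside the window. The aim is stated only in bullets 1 and 3, which meet it for AEs. The natural reading of the exception is the narrow one, since the broad reading would leave the default almost nothing but events without an end date. What remains is that the trigger is undefined.

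None of this answers the main point: for a medication known to predate vaccination and continuing past it, the rule as written gives a wrong date.

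**Conclusion.** Wrong as written, but minor. Bullets 1 and 3 assign a Day 0 start to any medication whose known month or year precedes vaccination and which is ongoing or ends after Day 0. That follows from the rule itself and does not depend on the assumed Day 0 dates. Such a drug would appear wrongly as new in the SAP 6.2 listing, provided the listing uses imputed dates. The number of records cannot be estimated from the documents. No immunogenicity result depends on it.

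The conflict between bullets 2 and 3 is real for years before the vaccination year. The exception in bullet 4 is a wording gap. It would affect the 21-day AE dataset only under the broad reading, and the day figures shown for it rest on the assumed Day 0 range.

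**What to change.** In SAP 12.5:

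1. Impute Day 0 only when the known month and year (or the known year, if the month is missing) is that of vaccination.
2. If the known period is earlier, impute its first day and treat the record as pre-vaccination.
3. If the known period is later, impute its first day, as now.
4. State which of the second and third bullets governs when only the year is known.
5. Define the exception for a wholly missing onset as an end date before Day 0.

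The cost is a few sentences and a small programming change, with no new data. Caution is kept wherever the timing relative to vaccination is truly unknown. The change is best made before the Day 21 unblinding, because SAP 10 treats what is reported at that review as final.

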13 CHANGES TO ANALYSES SPECIFIED IN THE PROTOCOL

NA

14 CHANGES TO THE SAP

NA

15 **REFERENCES**

CDC (2017b). What you should know and do this Flu season if you are 65 years and older Retrieved June 27 2017 from https://www.cdc.gov/flu/about/disease/65over.htm.

Trial Day:	0	3	7 (Stage 1 ONLY) [8]	7 (Stage 2 ONLY) ^[8]	21	56	90	182	273	364		
Window (days):		±1	+1	±1	± 2	± 2	± 7	± 7	± 7	±14		
Trial Procedures												
Trial Informed Consent	Х											
Inclusion/Exclusion Criteria	Х											
Medical/Medication History	Х											
Physical Exam	Х		X ^[7]		X ^[7]	X ^[7]		X ^[7]		X ^[7]		
Vital Signs	X [1]		Х		X [1]	Х		Х		Х		
Clinical Safety Laboratory ^[2]	Х				Х							
Serology	Х				Х							
Trial Treatment Injection	X											
Rescue Injection with a licensed seasonal influenza vaccine ^[6]					Х							
Adverse Event Review ^[4]	Х	X ^[3]	Х	X ^[3]	Х	Х	Х	X	Х	Х		
Concomitant Medications Review ^[4]	X	X	X	х	X	X	х	X	X	Х		
Subject Diary Review		X ^[3]	X ^[5]	X ^[3]	X ^[5]							

Appendix 1 – TNIV-E-101 TRIAL PROCEDURES SCHEDULE

Note: Procedures shaded in grey are performed via scripted telephone call.

^[1] Vital signs to be captured pre-vaccination and between 30 to 60 minutes post-vaccination.

^[2] Includes assessments for hematology (complete blood count [CBC] with hemoglobin, hematocrit, red blood cell [RBC] count, platelet count, and white blood cell [WBC] count with differential) and serum chemistry (alanine aminotransferase [ALT], aspartate aminotransferase [AST], total bilirubin, alkaline phosphatase, creatinine, and blood urea nitrogen [BUN]).

^[3] Subjects will be asked to report any grade 3 solicited or unsolicited adverse event or SAE experienced since the last visit and may be asked to return to the clinic for an unscheduled visit to evaluate the event(s) at the Investigator's discretion.

^[4] All adverse events and concomitant medications taken will be collected through Day 21; thereafter only MAEs, SAEs, and SNMCs and medications taken for these events will be collected.

^[5] The subject diary will be reviewed by the investigator and collected at the Day 7 visit (Stage 1 subjects ONLY) or Day 21 visit (Stage 2 subjects ONLY).

^[6] On Day 21, all Group A and B subjects will be administered a rescue injection with a licensed influenza vaccine, and all Group C subjects will be administered an injection of saline placebo to maintain trial blind. Subjects should be free of acute illness (defined as the presence of a moderate or severe illness with or without fever, or an oral temperature $\geq 38.0^{\circ}$ C) in order to receive the second vaccination. Subjects presenting with an acute illness on Day 21 may return to the study site within the next 7 days to receive their 2nd vaccination. If a subject has experienced any AEs/SAE between study Days 0 and 21, then Day 21 vaccination may be administered or delayed for up to 7 days based on the Investigator's discretion.

^[7] If needed, a physical examination may be performed, based on the investigator's discretion.

^[8] All Stage 1 subjects will be required to complete a Day 7 in-clinic visit to present their subject diaries, whereas Stage 2 subjects will be required to complete a safety telephone call.
